#### **9.2.3. Summaries of Serious Adverse Events (SAE), Adverse Event Dropouts, and Death**

For the 24-Week Analysis and the Final Analysis the number and percentage of subjects with serious treatment emergent AEs reported will be summarized by MedDRA system organ class and preferred term within each starting dose group and all treated subjects without regard to intensity or relationship to study drug. The SOCs will appear in descending order of number of subjects in the two treatment groups combined, i.e., all treated subjects, with at least one SAE mapped to the SOC. The PTs within each SOC will appear in descending order of number of subjects in the two treatment groups combined with at least one SAE mapped to the PT within that SOC.

The same types of tables as described for SAEs will be produced for:

- TEAEs leading to treatment discontinuation and
- TEAEs leading to deaths

A by subject adverse events listing will be produced to support these three tables. The list for the 24-Week Analysis will show all AEs for subjects who had at least one SAE or had treatment discontinued due to a TEAE or had a TEAE that led to death during the Dose Titration Period by starting dose group and subject number with the subject's AEs listed in chronological order of AE start date. Similarly, the list for the Final Analysis will be produced to show the AEs for subjects who experienced the same types of AEs either in the Dose Titration or Dose Maintenance period.

A listing of all adverse events of each deceased subject will be produced.

---

Document: \\quintiles.net\enterprise\apps\sasdata\sasb\sas\Keryx\KRX-0502\Biostatistics\Documentation\SAP\

### **9.3. Total Duration of Therapy, Maximum Daily Dose, Final Daily Dose of Study Medication, and Compliance**

For the 24-Week Analysis, a table will be provided that shows the descriptive statistics for subject's total duration of exposure in days, average and maximum daily dose attained, final daily dose taken, and the number and percentage of subjects with overall compliance during the Dose Titration Period in the two categories, < 50% and >=50%, by starting dose treatment groups and for the four dose sequence treatment groups.

A by subject listing for exposure, dosing and compliance will be provided for support in determining members of the PP Analysis set for the Final analysis.

For the Final Analysis, a table will be provided corresponding to that described for the 24-Week Analysis except that along with the descriptive statistics for the Dose Titration Period those for the Dose Maintenance Period and the entire study will be included. The Final Analysis listing will include the data for all visits within the study and total duration of exposure at Week 48 and overall compliance for the entire study along with the other variables on the listing produced for the 24-Week Analysis.

#### **9.3.1. Total Duration of Exposure Calculation**

A subject's total duration of exposure in days is the total number of days that the subject was prescribed to be taking more than zero pills per day.

For this study, duration of exposure in days for a subject is defined as the subject's first dose date minus last dose date plus 1 day minus the number of days that the subject was using a prescribed study drug interruption, i.e., using a dose of zero pills per day as prescribed.

For the Dose Titration Period a subject's:

duration of exposure (days) during the Dose Titration Period

=

([minimum of the subject's Week 24 visit date and date of last dose in the period] – first dose date + 1 day)

–  $\sum_{i=1}^k ([actual\ stop\ date]_i - [actual\ start\ date]_i + 1)$

where  $i$  denotes the  $i^{\text{th}}$  time during the Dose Titration Period that the subject was prescribed zero pills per day, the  $i^{\text{th}}$  actual start date and  $i^{\text{th}}$  actual stop date are the first and last dates that the subject was taking zero pills during the period for which the  $i^{\text{th}}$  prescription of zero pills per day was in effect.

For the Dose Maintenance Period a subject's:

duration of exposure (days) during the Dose Maintenance Period

=

(last dose date – Dose Maintenance Period first dose date + 1)

–  $\sum_{i=1}^k ([actual\ stop\ date]_i - [actual\ start\ date]_i + 1)$

where  $i$  denotes the  $i^{\text{th}}$  time during the Dose Maintenance Period that the subject was prescribed zero pills per day, the  $i^{\text{th}}$  actual start date and  $i^{\text{th}}$  actual stop date are the first and last dates that the subject was taking zero pills during the period for which the  $i^{\text{th}}$  prescription of zero pills per day was in effect.

Total duration of exposure (days) for the entire study

=

Total duration of exposure (days) during the Dose Titration Period

+

Total duration of exposure (days) during the Dose Maintenance Period.

Note: Duration of exposure in months = duration of exposure in days divided by 30.4375.

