7.5.2. Unscheduled Dose Adjustments

Unscheduled dose adjustments may be necessary at any point during the study. Below guidance and the dosing algorithms depicted in [Figure 2](#), [Figure 3](#), and [Figure 4](#) aim to assist the Investigator with decision making about dose modification in the presence of laboratory abnormalities or AEs. They are not intended to define a standard of care, nor should they be interpreted as prescribing an exclusive course of management. Investigators are responsible for evaluating the appropriateness of applying these guidelines to any particular clinical situation for an individual subject. Dose interruption refers to holding of the drug, usually for a short term with the intent to resume dosing when possible. To discuss dosing decisions, including extended dose interruption, Investigators should contact the Medical Monitor.

- Serum phosphorus <2.5 mg/dL:
 - If serum phosphorus is <2.0 mg/dL, interrupt dosing.
 - Two weeks after interrupting the dose, repeat the laboratory tests:
 - If serum phosphorus is ≥ 2.5 mg/dL, resume dosing at the dose prior to the dose interruption.
 - If serum phosphorus is ≥ 2.0 to <2.5 mg/dL, resume dosing at a reduced dose compared to the dose prior to the dose interruption.
 - If serum phosphorus is <2.0 , continue dose interruption.
- If serum phosphorus is ≥ 2.0 to <2.5 mg/dL, reduce the KRX-0502 dose by 1 to 3 tablets/day without complete dose interruption.
 - Two weeks after reducing the dose, repeat the laboratory tests:
 - If serum phosphorus is ≥ 2.5 mg/dL, increase the dose to the dose prior to the dose reduction.

- If serum phosphorus is ≥ 2.0 to < 2.5 mg/dL, reduce the dose again.
- If serum phosphorus is < 2.0 mg/dL, interrupt dosing.
- Decisions about resuming or increasing dosing and at which dose should take into consideration the absolute levels and trends of the serum phosphorus in the context of the prior dose changes as well as Hgb and TSAT.
- After resolution of a low serum phosphorus, an attempt should be made to increase the dose to the highest dose tolerated prior to the dose interruption or reduction, if supported by the Investigator's clinical judgement.

TSAT $\geq 50\%$:

- If TSAT is $\geq 50\%$, repeat laboratory tests with care to assure that the blood draw is performed before dosing with KRX-0502.
 - If the repeat TSAT is $\geq 70\%$, interrupt dosing.
 - If the repeat TSAT is ≥ 50 and $< 70\%$, the response should consider the Hgb level.

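### SAP 9.3.1 subtracts recorded interruption days that fall outside the exposure span, so a hold with no resumption inside the period can make exposure too short, zero or negative

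*SAP*

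**What the plan says.** SAP 9.3.1 opens by defining a subject's exposure as the "total number of days that the subject was prescribed to be taking more than zero pills per day". It then gives a working rule: the span between first and last dose plus one day, "minus the number of days that the subject was using a prescribed study drug interruption".

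The two displayed formulas apply this rule by period:

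- **Dose Titration Period.** The span ends at the "minimum of the subject's Week 24 visit date and date of last dose in the period". The sum subtracted from it runs over each "time during the Dose Titration Period that the subject was prescribed zero pills per day".
- **Dose Maintenance Period.** The span is "last dose date – Dose Maintenance Period first dose date + 1". The sum runs over each "time during the Dose Maintenance Period that the subject was prescribed zero pills per day".

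In both, the start and stop dates of an interval "are the first and last dates that the subject was taking zero pills during the period for which the" zero-pill prescription was in effect. The section does not limit those dates to the span, set a floor at zero, or say what stop date to use for a hold that never ends.

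The resulting days feed the subject-months of exposure in the tolerability summary (SAP 9.1) and the exposure table (SAP 9.3).

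**The concern.** The two parts of the formula cover different stretches of time. The span excludes everything after the last dose. The subtraction reaches as far as the recorded stop date of each hold. A hold that is never followed by another dose lies wholly after the last dose, so its days are outside the span already and the sum removes them again. The same happens in the titration formula when a hold begins before the Week 24 visit and ends after it.

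Such a hold is foreseeable. For low phosphorus, Protocol 7.5.2 says: "Two weeks after interrupting the dose, repeat the laboratory tests". It allows the hold to continue after that test, and for elevated TSAT it provides a further repeat two weeks later. It describes resumption as intended when possible, and Protocol 8.3.1 lists adverse events among the reasons for permanent discontinuation.

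At stake is the accuracy of the exposure summaries for subjects whose drug was held and then stopped, a group that matters in a tolerability table. An impossible value could also appear as a table minimum.

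**Working it through.** The SAP gives no worked exposure figure to reproduce, so the check compares its formula with its own definition.

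**Inputs.** Days are counted from the first dose (day 1). The Week 24 visit is placed at day 168: study day 169 in SAP Table 2, with the first dose on study day 2. All dose and hold dates are assumptions. Only the two-week and repeated two-week re-test intervals come from Protocol 7.5.2.

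**Formula as written:** (span end − period first dose + 1) − Σ(stop − start + 1).

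**Comparator:** days prescribed more than zero pills, from the SAP's opening definition.

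| Case | Formula as written | Definition |
|---|---|---|
| Hold days 57–70, resumes, last dose day 167 | 167 − 14 = 153 | 153 |
| Last dose day 28, terminal hold 29–42 | 28 − 14 = 14 | 28 |
| Last dose day 84, terminal hold 85–98 | 84 − 14 = 70 | 84 |
| Last dose day 84, terminal hold 85–112 | 84 − 28 = 56 | 84 |
| Last dose day 28, terminal hold 29–56 | 28 − 28 = 0 | 28 |
| Last dose day 14, terminal hold 15–42 | 14 − 28 = −14 | 14 |
| Hold 155–182 across the Week 24 visit, last titration dose day 154 | 154 − 28 = 126 | 154 |
| Maintenance: doses 169–182, terminal hold 183–210 | (182 − 169 + 1) − 28 = −14 | 14 |

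In general, a hold of h days lying wholly after the span understates exposure by h days. With no other hold, the result is zero when h equals the days dosed and negative when h exceeds them. The first row shows that a subject who resumes within the period is computed correctly.

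**Bounded subtraction:** Σ max(0, min(stop, span end) − max(start, period first dose) + 1).

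- Resuming subject: min(70, 167) − max(57, 1) + 1 = 14, so 167 − 14 = 153.
- 28 days dosed, 14-day terminal hold: min(42, 28) − max(29, 1) + 1 = 0, so 28.
- Hold across Week 24, titration side: min(182, 154) − max(155, 1) + 1 = 0, so 154.

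**Why the lower bound is needed.** Continue the last case with an assumed first maintenance dose on day 183 and last dose on day 335. The span is 335 − 183 + 1 = 153 days. If the hold is also assigned to maintenance, subtracting all of it gives 153 − 28 = 125. Cutting it at the visit and subtracting only days 169–182 gives 153 − 14 = 139. With the lower bound, min(182, 335) − max(155, 183) + 1 = 0, so 153, which is correct. Splitting at Week 24 alone would not be enough.

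**The case against.** The strongest reply is that the governing definition comes first and is right, and that a sensible programmer would read the working rule as removing interruption days inside the span. The definition does show what was meant. But the displayed formulas give explicit start and stop dates for each interval and tie them to the prescription, not to the span. Followed as written, they depart from the definition.

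The second reply stands and limits the claim. The error needs a hold that became permanent to be recorded as an interruption with a stop date after the last dose. The protocol distinguishes interruption from permanent discontinuation, and the documents do not say how such a hold is recorded. If no record extends past the last dose, nothing is lost. If the stop date is missing, the formula is undefined. A reader might infer that the exposure tables are biased low outright; the documents support only that they would be low for subjects whose holds are recorded this way.

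Three further limits stand:

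- Protocol 10.5 admits to maintenance only subjects who complete the Week 24 visit while on study drug. Whether a held subject qualifies is unclear, so holds spanning both periods may be uncommon. SAP section 9 restricts the 24-Week Analysis to treatment days before that visit, which limits what is counted but does not cap what is subtracted.
- Very early long holds are less well supported. Ten days dosed and a 28-day hold would give 10 − 28 = −18, but a hold that early would ordinarily need an adverse event or unscheduled test, because the first scheduled laboratory visit after dosing begins is Week 2.
- A reader might infer that efficacy or Per Protocol membership is affected. Neither is: compliance (SAP 9.3.2) has its own denominator, and SAP 9.1 lists subject-months beside counts and percentages without exposure-adjusted rates.

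**Conclusion.** The point holds in conditional form. Where a hold is recorded with a stop date after the end of the exposure span, SAP 9.3.1 removes days that were never counted. Exposure is understated by exactly those days, contrary to the section's own definition, and can reach zero or below. A two-week terminal hold costs 14 days and a four-week one 28.

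The number of affected subjects cannot be known from the documents. For scale only, assume 5 to 20 such holds of 14 to 28 days among 200 subjects with mean exposure of 200 to 336 days. The loss is then 5 × 14 = 70 to 20 × 28 = 560 days, out of 200 × 200 = 40,000 to 200 × 336 = 67,200. That is about 0.1% (70/67,200) to 1.4% (560/40,000) of total exposure. The aggregate effect would be small; the visible problem would be individual values and table minima. This is a minor correction to descriptive safety tables.

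**What to change.** In both period formulas of SAP 9.3.1, subtract only interruption days that fall between that period's first dose date and the end of that period's exposure span. The span ends at the earlier of the Week 24 visit and the last dose in the period for titration, and at the last dose date for maintenance. As a formula, replace the sum with Σ max(0, min(stop, span end) − max(start, period first dose) + 1). No separate rule for splitting a hold at Week 24 is then needed.

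Add a convention for a hold with no recorded stop date: treat it as running to the span end. In the same edit, correct the order of the dates in the prose sentence, which takes first dose minus last dose; the displayed formulas already have it right.

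The cost is a sentence or two in the SAP and a MIN/MAX bound in the exposure program. No new data are needed.

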### 9.3.2. Compliance Calculation

A subject's compliance to treatment during a specific time period expressed as a percentage is equal to 100 times the amount of study drug taken by the subject during the specific time period divided by the amount that was prescribed to be taken by the subject during the specific time period.

The number of pills recorded in the eCRF drug accountability pages as the number of pills dispensed and/or the number of pills returned at each site visit are based on a count of the physical pills in the bottle(s) dispensed and/or returned during the visit, respectively.

A subject's prescription may be changed at any time during the course of this study based on adverse events or certain laboratory test results observed or reported at any scheduled visit or any unscheduled visit. Additionally, it is planned that each subject will get the study drug dose titrated at the scheduled Week 12 visit. The prescribed amount to be taken starting after the scheduled Week 12 visit will depend on the Week 12 Hgb value.

The results of some laboratory tests will be required to make the decision regarding each study drug prescription during the study but these results will not be immediately available to the site on the visit day. Therefore, it may not be possible to confirm the number of pills actually in the bottle at the time that a new dose is prescribed to start. (Instructions with respect to a prescribed dose change may be delivered via telephone.)

The general expression for calculating a subject's compliance (%) over a specific time period X,

$$100 * \frac{\text{amount of study drug taken during the specific time period, } X}{\text{amount of study drug prescribed to be taken during the specific time period, } X}$$

using the drug accountability data recorded in the eCRF is expressed as

$$100 * \frac{(\# \text{ of pills dispensed at start of period } X - \# \text{ of pills returned at end of the period } X)}{(\# \text{ days in period } X) * (\# \text{ pills prescribed to be taken per day during the period } X)}$$

This expression for compliance will take one of three forms depending on the number of dose adjustments made between two successive site visits, i.e., zero, one or more than one dose adjustments.

To define compliance (%) for these three cases, the following notation and assumptions are made:

- Let the subscript  $k \geq 2$  denote the site visit number where:
  - $k = 2$  for the Randomization Visit, i.e., Visit 2 in the Schedule of Assessments (See protocol section 7 Table 2.);
  - $k = 3$  for the subject's next site visit, scheduled or unscheduled, after Visit 2;
  - $k = 4$  for the subject's next site visit, scheduled or unscheduled, after Visit(k = 3);
  - $k = 5$  for the subject's next site visit, scheduled or unscheduled, after Visit(k = 4);
  - ...
  - $k = j$  for the subject's next site visit, scheduled or unscheduled, after Visit(k = j-1).
- First dose on a new prescription issued on date of site visit is to be taken on the day after the site visit. E.g., a subject's 1st bottle of pills is dispensed on the Date of Visit 2 but the first pill is prescribed to be taken on the day after Visit 2.
- In general, because visits should be scheduled to occur in the morning, non-fasted and subjects are instructed to hold study drug until blood is drawn, assume that pills

consumed on the date of a site visit are at the dose level last prescribed before the site visit.

To calculate compliance between any two successive site visits one of the three cases described below are applicable.

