10.6. Visits 10 to 12 (Weeks 32 to 48) – Dose Maintenance Period

Only subjects who complete the 24-week Dose Titration Period will be eligible to enter the Dose Maintenance Period following Week 24.

During the Dose Maintenance Period, subjects will continue on the dose determined during the Dose Titration Period. There will be no scheduled dose adjustment other than that on Week 12. If an unscheduled dose reduction or interruption is necessary due to an AE or abnormal laboratory value, the dose may be subsequently increased back to the previous dose upon resolution of the event/laboratory abnormality.

Instructions for unscheduled dose interruption ([Section 7.5.2](#)) and reduction, dose resumption, and dose increase ([Section 7.5](#)), as the case may be, apply also to the Dose Maintenance Period.

If an unscheduled dose reduction or interruption is necessary due to an AE or an abnormal laboratory value, upon resolution of the laboratory abnormality or AE the dose should be resumed and/or subsequently increased to the highest dose tolerated prior to dose reduction or interruption, if supported by the Investigator's clinical judgement.

Visits need to occur in the morning, non-fasted and subjects instructed to hold KRX-0502 until blood is drawn. The morning dose can be taken after the blood draw with a snack or with the next meal.

10.6.1. Procedures for Visits 10 and 11

- Record vital signs
- Review laboratory results from previous visit
- Record AEs
- Record changes in concomitant medications or non-drug therapies
- Review whether any non-permitted medications were administered since the last visit (see [Section 9.2.1](#) and [Section 9.2.2](#))
- Instruct subject about non-permitted medications (see Section 9.2.1 and Section 9.2.2)
- Record hospitalizations and duration
- Obtain blood samples:

- CBC (every visit)
- CCP (every visit)
- Iron studies (every visit)
- Record study drug dosing, review diary, and assess study drug compliance (every visit)
- Dispense study drug
- Schedule next visit for AM and instruct subject to hold KRX-0502 until blood is drawn (see [Section 7.1](#))

For dosing and dose adjustment criteria, see [Section 7.5](#).

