#### Compliance Over Period Spanning More Than Two Consecutive Site Visits:

To calculate compliance for any period X that spans more than the period between two consecutive site visits note that the numerator in the expression,

Compliance (%) =

$$100 * \frac{\text{amount of study drug taken during the specific time period, } X}{\text{amount of study drug prescribed to be taken during the specific time period, } X}$$

is 100 times  $\sum_{k=3}^n$  (# pills dispensed at  $\text{Visit}(k - 1) - \# \text{ pills returned at } \text{Visit}(k))$ , where n - 1 is the number of site visits the subject had during the period X and the denominator is

$\sum_{k=3}^n$  (the number of pills *prescribed to be taken from*  $\text{Visit}(k - 1)$  thru the day before  $\text{Visit}(k))$

where (the number of pills *prescribed to be taken from*  $\text{Visit}(k - 1)$  thru the day before  $\text{Visit}(k)$ )

is the denominator of the expression given above for Case 1, Case 2 or Case 3 depending on the number of dose adjustments between  $\text{Visit}(k - 1)$  and  $\text{Visit}(k)$ .

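### The SAP's sum for compliance over a period always starts at Randomization, which contradicts its own definition of compliance for the Dose Maintenance Period

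*SAP*

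**What the plan says.** SAP 9.3.2 defines compliance in words as the drug taken in a stated period divided by the drug prescribed in that period. It then sets up a visit index: k = 2 stands "for the Randomization Visit, i.e., Visit 2 in the Schedule of Assessments", k = 3 stands "for the subject's next site visit, scheduled or unscheduled, after Visit 2", and each later visit takes the next number. Nothing restarts the index for a later period.

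The last part of 9.3.2 covers periods longer than one between-visit interval. It opens "To calculate compliance for any period X that spans more than the period between two consecutive site visits note that the numerator in the expression" for compliance, and gives both numerator and denominator as sums from k = 3 to n, where "n - 1 is the number of site visits the subject had during the period X".

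SAP 9.3 says where such figures are needed. The 24-Week table shows "the number and percentage of subjects with overall compliance during the Dose Titration Period in the two categories, < 50% and >=50" percent. The Final Analysis table is to correspond to it, except that "along with the descriptive statistics for the Dose Titration Period those for the Dose Maintenance Period and the entire study will be included".

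**The concern.** The index is absolute and the lower limit of the sum is fixed at 3, so the first term is always pills dispensed at Randomization minus pills returned at the next visit, whatever X is. The number of visits in X moves only the upper limit. For a period that starts at Week 24, the sum has about the right number of terms but takes them from the wrong end of the trial.

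The neighbouring exposure formula in SAP 9.3.1 is anchored correctly, to the first dose date of the Dose Maintenance Period. Applied to the letter, the Final Analysis table would set Maintenance exposure from Weeks 24 to 48 beside Maintenance compliance from the first weeks of treatment. The stated objective is long-term efficacy and safety of the regimens, so adherence in the second half is worth reporting correctly.

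**Working it through.** **Inputs.**
- Index rule and sum limits: SAP 9.3.2, so n = (number of site visits in X) + 1.
- Target study days (SAP Table 2): Visit 2 = 1, Visit 3 = 15, Visit 4 = 29, Visit 5 = 57, Visit 6 = 85, Visit 7 = 113, Visit 8 = 141, Visit 9 = 169, Visit 10 = 225, Visit 11 = 281, Visit 12 = 337.
- Period membership: Protocol 10.5 makes Visit 9 (Week 24) the last Titration visit, with drug dispensed there. Protocol 10.6 is headed "Visits 10 to 12 (Weeks 32 to 48) – Dose Maintenance Period".

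The SAP gives no numerical compliance result to reproduce. The check is to expand the sum for each period, with scheduled visits only, so that k equals the visit number.

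| Period | Visits counted | n | Terms | Weeks covered | Correct? |
|---|---|---|---|---|---|
| Dose Titration | 2 to 9 (8) | 9 | k = 3 to 9 | 0 to 24 | yes |
| Entire study | 2 to 12 (11) | 12 | k = 3 to 12 | 0 to 48 | yes |
| Dose Maintenance, Week 24 visit counted | 9 to 12 (4) | 5 | k = 3 to 5 | 0 to 8 | no |
| Dose Maintenance, Week 24 visit not counted | 10 to 12 (3) | 4 | k = 3 to 4 | 0 to 4 | no |

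The first two rows show that the rule works when both end visits are counted. The same counting gives Weeks 0 to 8 for Maintenance.

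**Unscheduled visits.** These also take index numbers, so the span varies by subject. With two extra Maintenance visits and none earlier, there are 6 visits, n = 7, and the sum covers Weeks 0 to 16. With no unscheduled Titration visits, a pill count from after Week 24 enters only if n is at least 10, that is, with at least 9 visits counted. Even then the sum starts at Randomization.

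**Illustration (adherence values assumed).** A subject on the 3-6 tablets/day sequence takes the new dose from the day after Week 12, has scheduled visits only, and takes 100% of tablets to Week 24 and 40% afterwards.

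- Prescribed in Weeks 0 to 8, by the SAP's Case 1: (15 − 1 − 1) × 3 = 39; 3 + (29 − 1 − 15) × 3 = 42; 3 + (57 − 1 − 29) × 3 = 84. Sum = 165.
- Prescribed in Weeks 24 to 48: 168 days × 6 = 1008.
- Maintenance compliance by the literal sum: 100 × 165/165 = 100%, category ≥50%.
- Maintenance compliance by the verbal definition: 100 × (0.40 × 1008)/1008 = 40%, category <50%.
- Whole study: Titration prescribes 39 + 42 + 84 + 84 + 165 + 168 + 168 = 750, so compliance is 100 × (750 + 403.2)/(750 + 1008) = 65.6%.

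**The case against.** The strongest reply is that the words settle the matter. The sums are introduced as the amounts taken and prescribed during X, and n is tied to visits within X, so the intent is plain. A programmer who used Week 0 to 8 bottles for Weeks 24 to 48 would have to override the definition. This stands: a reader might infer that the Maintenance column will come out wrong, and the documents do not support that as a settled outcome. They hold a definition and a formula that disagree. What remains is that following the formula gives a wrong figure, and that two programmers could resolve the conflict differently.

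A reader might also infer that a late fall in adherence would be hidden. It would not disappear. The whole-study figure includes the Maintenance pill counts, the Final Analysis listing covers all visits, and the between-visit calculations (Cases 1 to 3) are sound. The two broad categories could still blur it: the subject above is 65.6% over the whole study and so falls in the ≥50% class.

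Nor does the point reach the efficacy analyses. The Per Protocol exclusion in SAP 6.3.5 uses overall compliance from randomization, where the sum is right. The modified Per Protocol set in 6.3.6 ignores compliance.

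Finally, SAP 9.3 does not name Maintenance compliance outright. The listing text mentions only overall compliance for the entire study, so the requirement is inferred from the Final table corresponding to the 24-Week one. That inference is reasonable but is not an explicit statement.

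**Conclusion.** The point holds as a low-severity indexing error in the multi-visit part of SAP 9.3.2. The visit index itself is properly defined; the fault is in the sum limits that use it. For the Dose Maintenance Period they contradict the SAP's own definition and, with scheduled visits only, select Weeks 0 to 8 or Weeks 0 to 4 according to whether the Week 24 visit is counted. Unscheduled visits alter the span but not its start.

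One descriptive column is at stake. The conclusion rests on reading the index as absolute, which the text supports, and on Maintenance compliance being part of the Final Analysis table, which is probable. The change from 40% to 100% depends on assumed adherence; the selection of the wrong period does not.

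**What to change.** In the multi-visit part of SAP 9.3.2, change the limits of both sums to k = a + 1 to b. Define a and b as the indices of the subject's first and last site visits bounding period X. For Titration and the entire study, a is the Randomization visit; for Maintenance, a is the Week 24 visit, where drug for that period is dispensed.

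Replace only the clause that defines n. The SAP's wording there runs "where n - 1 is the number of site visits the subject had during the period X and the denominator is", so removing the whole sentence would also remove the introduction to the denominator.

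With scheduled visits the Maintenance sum then runs over k = 10 to 12, Weeks 24 to 48, and the other two periods keep their present terms. The cost is one line of wording and a check that the compliance program uses the same limits. No extra data are needed.
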